After bringing the variables to the normal distribution, the statistical significance was found in the control group only (Table 8).

Table 8. Statistical analysis of normally distributed antiphospholipid antibody levels.

	95% CI	p-value (t-student)
Main group, IgM	-0,03; 0,11	0,185
Main group, IgG	-0,07; 0,11	0,726
Control group, IgM	0,04; 0,14	0,001
Control group, IgG	0,05; 0,15	0,0001

ANOVA was performed to determine the direct effect of the natural food product on the aPL values (Table 9). ANOVA did not reveal any statistical significances.

Table 9. Finding the effect of the freeze-dried mare's milk on the antiphospholipid antibody values (ANOVA - analysis of variance).

Antibody name	p (One-way ANOVA)
IgM	0,541
IgG	0,938

aPL values in almost all patients of both groups were ranged normally. The intersection of all confidence intervals of medians and means indicates the absence of statistical significance between these indicators. The results before and after bringing the aPL values to normal distribution differ greatly, especially for the IgM level in the main group. One-factor analysis of variance also showed the lack of significance of the studied factor. These several theses can explain the given results. First, initial aPL values could have been normalized over 6-9 months after COVID-19. Second, there were screening kits in the study. Therefore, the obtained results do not show the levels of specific phospholipids (phosphatidylcholine, phosphatidylethanolamine, aCL, anti- β 2-GP1, etc.). Third, the severity of COVID-19 was not considered as an inclusion criterion.

Quality of life analysis.

The quality of life of post-COVID patients in the main group statistically significantly improved in both physical and mental health components after using mare's milk. In the control group, there was no statistically significant change in quality-of-life indicators for both physical and mental health components. Even though the average score for the physical component in the control group is higher than in the main group, the level of statistical significance and the confidence interval of both groups allow us to conclude that freeze-dried mare's milk can have a positive effect on this indicator of the quality of life of post-COVID patients (Table 10).

Table 10. The average quality-of-life score in patients of the main and control groups.

	Quality-of-life components							
	Physical				Mental			

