1. Based on the results of gut microbiome sequencing, ELISA (antiphospholipid antibodies), and biochemical blood analysis in the main and control groups, we determine the dynamic changes of those parameters during COVID-19 rehabilitation.
2. According to the results, the effectiveness of Saumal itself regarding these 2 parameters will be evaluated.
3. Develop recommendations and an algorithm for patient management after COVID-19 to prevent complications.

Study Design

Study Type: Interventional

Primary Purpose: Treatment

Interventional Study Model: Parallel Assignment

Number of Arms: 2

Masking: None (Open Label)

Allocation: Randomized

Enrollment: **60 patients.** Originally, we planned to include 38 patients in the main group and 37 in the control group. Overall, these groups were evenly divided, with 30 patients in each group.

Arms and Interventions

Arms	Assigned Interventions
Experimental: Main Group Patients who had suffered from COVID-19 in the six months before the start of the study. Patients will receive Saumal (freeze-dried mare milk) for four weeks.	Dietary Supplement: Freeze-dried Mare Milk (Saumal) Freeze-dried Mare Milk (Saumal) is frequently reported for having therapeutic and dietary properties associated with specific chemical composition and certain physical properties of the product. It contains a total of about 40 biologically active components, the most important of them vitamins A, C, B1, B2, B6, and B12, amino acids, enzymes, and trace elements (low molecular weight peptides, lactalbumins, and globulins). Saumal will be administered to patients at a dose of 25 grams of dry powder per 200 ml of water, 2 times a day, 30 minutes before the meal, for 4 weeks.
No Intervention: Control Group Patients who had suffered from COVID-19 in the six months before the start of the study. There will be no intervention.	

Eligibility

Minimum Age: 18 Years

Maximum Age: 75 Years

Sex: All

Gender Based: No

Accepts Healthy Volunteers: No

Inclusion Criteria:

Age 18 years and older;

Patients in rehabilitation after COVID-19;

Signed informed consent;

Presence of patient's history of COVID-19, reliably established by PCR+ /presence of IgG/ diagnosis of coronavirus pneumonia on Computer Tomography based on discharge from hospital or outpatient records.

Exclusion Criteria:

Chronic inflammatory bowel disease;
Gut microbiota transplantation;
Chronic pancreatic disease, period of exacerbation;
Liver cirrhosis, Metavir stage 3-4;

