Any disease in the decompensation stage;
Neuralgic and psychological disorders that interfere with the study;
Cancer;
Non-transportable patients;
Patients who do not reside in Almaty;
Patients who have refused to participate in the study.

Examined for eligibility - 76 people;

Confirmed eligible - 60 people. According to our strict exclusion criteria, we had to remove 16 people [8 – oncological patients, 5 – moved house, 3 patients refused to participate];

Included in the study - 60 patients;

Completing follow-up and analysed - 60 patients.

Statistical Analysis Plan

Gut microbiota:

IBM SPSS ver. 23.0 (Chicago, IL, USA) was used to determine the statistical significance of the obtained data. All the indicators were verified for compliance with the law on normal distribution. If the variables obeyed this law, the Student's paired t-test was applied to determine statistical significance between the values before and after milk intake. Otherwise, the Wilcoxon sign rank criterion was used.

A single-factor analysis of variance was employed to verify the effect of administering freeze-dried mare's milk, which could potentially affect the indicators of gut microbiota.

Antiphospholipid antibodies:

The 95% confidence interval for aPL value was calculated for both median and mean. The confidence interval for the latter one was calculated in the descriptive statistics menu in IBM SPSS ver. 23.0 (Chicago, IL, USA).

It is necessary to find the value of the confidence coefficient (Student's criterion (t)) in the table of critical t-values, considering the total number of respondents (n) to find out a confidence interval for the median with a given confidence probability (p). After that, the calculation of the natural integer number (C) is needed for such a probability value: $C_p = (n/2 - t(p) \sqrt{n}/2)$. The lower confidence limit for the median is $X (C_p)$, where X is the ordinal number of the value in the ranked variation series corresponding to the lower boundary of the confidence interval. The upper confidence limit for the median is $X (n + 1 - C_p)$, where X is the ordinal number of the value in

the ranked variation series corresponding to the upper boundary of the confidence interval.

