The proportion of Bacteroidetes and Firmicutes in the gut microbiota is most significant. Summarizing their values in the main and control groups, we can see that their content increased in the former and decreased in the latter. Statistical analysis revealed a significant difference in the content of these phyla between the main group compared to the control group (Table 3).

Table 3. The percentage terms of Bacteroidetes and Firmicutes phylum in the main and control groups.

Main group			Control group		
Bacteroidete s+Firmicutes (before)	Bacteroidetes +Firmicutes (after)	p (Wilcoxon)	Bacteroidete s+Firmicutes (first test)	Bacteroidetes +Firmicutes (second test)	p (Wilcoxon)
77,63%	81,3%	0,026	78,76%	75,87%	0,213

To determine the effect of freeze-dried mare's milk on the gut microbiota at the phylum level, a one-factor analysis of variance was performed. A statistically significant relationship between such a factor as the administration of freeze-dried mare's milk was revealed in the Firmicutes, Elusimicrobia and Proteobacteria phyla (Table 4).

Table 4. The relationship between the use of prescribed freeze-dried mare's milk and indicators of gut microbiota at the phylum level.

Phylum name	p (One-way ANOVA)
Bacteroidetes	0,180
Firmicutes	0,048
Proteobacteria	0,043
Actinobacteria	0,186
Euryaychaeota	0,403
Verrucomicrobia	0,583
Chloroflexi	0,220
Cyanobacteria	0,280
Spirochaetes	0,340
Nitrospirae	0,143
Tenericutes	0,657
Fusobacteria	0,140
Elusimicrobia	0,044
Bacteroidetes + Firmicutes	0,037

Overall, the intake of freeze-dried mare's milk by post-COVID patients primarily contributed to an increase in the content of the sum of two major phyla of gut microbiota — Bacteroides and Firmicutes, with the latter being particularly significant. There is also a notable decrease in the number of bacteria from the Proteobacteria phylum in the main group, which includes representatives of pathogenic microflora.

Antiphospholipid antibody analysis.

29 out of 30 main group patients (96.67%) had normal IgM and IgG levels before taking freeze-dried mare's milk. In the case of the control group, aPL levels were normal in all respondents. The aPL levels were normal in patients of both groups after the second ELISA (Table 5).

Table 5. Antiphospholipid antibody scores of each patient in the main and control groups after two assays (aPL -antiphospholipid antibodies).

Main group		Control group					
aPL (before)		aPL (after)		aPL (first assay)		aPL (second assay)	

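### The antiphospholipid discussion infers no significance from overlapping intervals, does not reconcile this with the significant control-arm change in Table 8, and gives no between-arm estimate with a confidence interval

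*Combined protocol and SAP*

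**What the plan says.** The Statistical Analysis Plan (Antiphospholipid antibodies) provides confidence intervals for means and medians, a paired t-test or Wilcoxon test of before against after, and a one-way ANOVA relating the milk factor to antibody levels in both groups. It does not say whether the ANOVA outcome is the second value or the change, or whether it is raw or transformed.

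The Results section (Antiphospholipid antibody analysis) then reports:

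- At entry, for the treated arm: "29 out of 30 main group patients (96.67%) had normal IgM and IgG levels before taking freeze-dried mare's milk".
- At entry, the untreated arm had no abnormal values at all: "In the case of the control group, aPL levels were normal in all respondents".
- At the second assay, no patient in either arm was abnormal: "The aPL levels were normal in patients of both groups after the second ELISA (Table 5").
- On transformed values: "After bringing the variables to the normal distribution, the statistical significance was found in the control group only (Table 8"). Control IgM is 0.04 to 0.14 (p=0.001) and control IgG 0.05 to 0.15 (p=0.0001). Main IgM is -0.03 to 0.11 (p=0.185) and main IgG -0.07 to 0.11 (p=0.726).
- In Table 9, ANOVA gives p=0.541 for IgM and p=0.938 for IgG.

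The discussion below Table 9 takes the overlap of the mean and median intervals as showing no significance. It adds: "One-factor analysis of variance also showed the lack of significance of the studied factor". It lists three possible explanations, the first being: "First, initial aPL values could have been normalized over 6-9 months after COVID-19". The other two are the use of screening kits and the absence of a severity criterion for entry.

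**The concern.** Three statements about the same data are not brought together: overlap said to show no significance, paired tests that are clearly significant in the control arm, and an ANOVA that is null. A reader is likely to conclude that milk was tested against antiphospholipid antibodies and had no effect.

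That conclusion needs a between-arm estimate precise enough to exclude effects of interest, and none is given. Assessing the impact of milk on these antibodies is a stated aim (Detailed Description, Stage II), so the answer should rest on the randomised comparison.

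**Working it through.** **1. Why overlap is not the test.** Take two means with equal standard errors and 95% intervals of ±1.96 SE. The intervals stop overlapping only when the means differ by 2 × 1.96 = 3.92 SE. A paired test is significant at 1.96 × √(2(1 − r)) SE, where r is the within-patient correlation. The documents do not give r. At r = 0 the threshold is 2.77 SE, and at r = 0.5 it is 1.96 SE. Overlap is therefore compatible with a significant paired change.

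**2. Reproducing Table 8.** The inputs are the printed intervals and 30 patients per arm (Study Design: "Overall, these groups were evenly divided, with 30 patients in each group"; Eligibility: "Completing follow-up and analysed - 60 patients"). Mean change is the interval midpoint, SE = half-width / t(0.975, 29) with t = 2.045, and p is two-sided on 29 df. The rounding range varies each limit by ±0.005.

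| Row | Mean | SE | t | p computed (rounding range) | p printed |
|---|---|---|---|---|---|
| Main IgM | 0.04 | 0.07/2.045 = 0.0342 | 1.17 | 0.25 (0.20 to 0.31) | 0.185 |
| Main IgG | 0.02 | 0.09/2.045 = 0.0440 | 0.45 | 0.65 (0.57 to 0.74) | 0.726 |
| Control IgM | 0.09 | 0.05/2.045 = 0.0244 | 3.68 | 0.0009 (0.0003 to 0.0023) | 0.001 |
| Control IgG | 0.10 | 0.05/2.045 = 0.0244 | 4.09 | 0.0003 (0.00009 to 0.00085) | 0.0001 |

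The control rows reproduce within rounding, IgG at the edge of its range. Main IgG also fits. Main IgM does not quite fit its own interval.

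**3. Difference in change, main minus control.** SE = √(SE_main² + SE_control²) from unrounded values, on 58 df with t(0.975, 58) = 2.002.

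- IgM: 0.04 − 0.09 = −0.05; SE 0.0421; t = −1.19; p about 0.24 (0.16 to 0.35 over rounding); 95% CI −0.05 ± 2.002 × 0.0421 = −0.13 to 0.03.
- IgG: 0.02 − 0.10 = −0.08; SE 0.0503; t = −1.59; p about 0.12 (0.08 to 0.17 over rounding); 95% CI −0.08 ± 2.002 × 0.0503 = −0.18 to 0.02.

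The misfit in main IgM changes little. If p=0.185 and the interval width are kept, t = 1.358 and the mean becomes 1.358 × 0.0342 = 0.046. The difference is then about −0.04, with p about 0.30. If p=0.185 and the midpoint are kept, the SE becomes 0.04/1.358 = 0.0295, and p for the difference is about 0.20.

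**4. Comparison with Table 9.** The ANOVA p-values of 0.541 and 0.938 lie outside 0.16 to 0.35 and 0.08 to 0.17. The ANOVA was therefore probably run on something other than the change analysed in Table 8.

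**5. Precision.** The difference detectable with 80% power is about 2.80 × SE: 2.80 × 0.0421 = 0.12 for IgM and 2.80 × 0.0503 = 0.14 for IgG. Both exceed the whole control-arm change (0.09 and 0.10).

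**6. Patients with raised values.** Normal at entry: 29 + 30 = 59 of 60. One patient (1.7%), in the main group, could move from abnormal to normal, and none in control.

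**7. Time since infection.** The discussion places the initial values after 6-9 months of recovery. The Detailed Description (Stage I) and the arms table put COVID-19 within the previous six months.

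**The case against.** The section already reports a null result, claims no benefit for these antibodies, says almost all values were normal, and notes that results differ greatly before and after transformation. The control-only finding is printed just above Table 8. This stands: nothing is hidden. What is missing is the between-arm estimate and a reading of the control change.

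It is tempting to say that the control change disproves the explanation that levels had already normalised. The documents do not support this. Control values were normal at both assays, so the change lay within the normal range, where drift, regression to the mean or assay variation could produce it. The 59 of 60 figure fits earlier normalisation, which is only a hedged first of three explanations.

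It is also tempting to read the pattern as unfavourable to milk, a fall without treatment that is smaller with it. Both between-arm intervals include zero and values on either side. The direction is also unconfirmed. Tables 1 and 10 follow before minus after, so a positive value would be a fall under an increasing transform, but the transform is not named in the text available to me, which lacks most of the content between the start of Table 5 and Table 8. A reciprocal would reverse the sign.

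Finally, the outcome is a continuous level, so a trial in patients with normal values is not uninformative. That also stands: the limit from 1 of 60 applies to raised antibodies only.

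**Conclusion.** The point holds as one about inference and reporting. The overlap argument is invalid and sits unreconciled beside two significant paired tests. The ANOVA outcome is undefined and its p-values do not match the change data. The implied between-arm differences, about -0.05 (-0.13 to 0.03) for IgM and -0.08 (-0.18 to 0.02) for IgG, leave the effect of milk within the normal range inconclusive. For raised antibodies the trial has almost no patients to inform an answer.

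The figures assume 30 complete pairs per arm, independent arms and the same transform in both. The last needs confirming, because Table 10 suggests it may not hold throughout the report. There, the main-group physical interval has midpoint (-7.34 - 1.56)/2 = -4.45, equal to 43.515 - 47.965. The control interval of -0.14 to 0.09 does not contain 50.451 - 50.797 = -0.346.

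A reader might infer that Table 9 is wrong. The documents do not show that, because an ANOVA on second values or on the raw scale could give those p-values.

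**What to change.** - Delete the inference from overlapping intervals.
- Report the between-arm difference for IgM and IgG with 95% CI, preferably adjusted for the baseline value already collected. State the transform, that it is the same in both arms, and the direction of the difference. Define the Table 9 outcome.
- Check the main-group IgM interval against its p-value.
- State that the control arm changed within the normal range, and that significance in one arm only is not evidence of a difference between arms.
- Replace the closing ANOVA sentence with wording such as: within the normal range the comparison is inconclusive; as 1 of 60 patients was abnormal at entry, the trial cannot show whether milk lowers raised antibodies.
- Keep prior normalisation as a possibility, but reconcile its 6-9 months with the six-month entry window.

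The cost is a short re-analysis of data in hand and one rewritten paragraph. The small downside is a less definite statement on these antibodies.

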If the normal distribution law is followed, the Student's paired t-test was used to determine statistical significance between values before and after freeze-dried mare's milk. If not, the Wilcoxon sign rank criterion was used for intergroup comparison. One-way analysis of variance (ANOVA) was used to determine the relationship between the mare's milk prescription factor and aPL levels in both groups.

Quality of life:

IBM SPSS ver. 23.0 (Chicago, IL, USA) was used to determine the statistical significance of the obtained data. All the indicators were verified for compliance with the law on normal distribution. If the variables obeyed this law, the Student's paired t-test was applied to determine statistical significance between the values before and after milk intake. Otherwise, the Wilcoxon sign rank criterion was used.

A single-factor analysis of variance was employed to verify the effect of administering freeze-dried mare's milk, which could potentially affect the quality-of-life scores.

Results section

Gut microbiota analysis.

In the main group, after taking freeze-dried mare's milk, there was a decrease in the content of bacteria phyla Bacteroidetes, Proteobacteria, Verrucomicrobia and Chloroflexi (by 3.03%, 2.83%, 0.47% and 0.16, respectively), and an increase in the content of bacteria phyla Nitrospirae, Tenericutes, Cyanobacteria, Spirochaetes, Euryarchaeota, Actinobacteria and Firmicutes (by 0.02 %, 0.05%, 0.15%, 0.17%, 0.24%, 1.42% and 7.62%, respectively).

The Fusobacteria phylum was absent according to the results of mare's milk intake in all respondents. The Elusimicrobia phylum, on the contrary, was present in some respondents as a result of therapy.

Attention is also drawn to the presence of the Synergistetes phylum, which was absent in the control group both before and after therapy. Moreover, the difference between the Firmicutes, Proteobacteria, Chloroflexi, Cyanobacteria and Synergistetes phyla was statistically significant (Table 1).

Table 1. The percentage terms of all phyla of the gut microbiota in the main group before and after taking freeze-dried mare's milk (CI - confidence interval).

Phylum name	Before	After	95% CI (t-student)	p (t-student)
Bacteroidetes	32,32%	29,43%	-0,01; 0,07	0,178
Firmicutes	45,31%	51,87%	-0,09; -0,02	0,001
Proteobacteria	9,25%	6,52%	0,1; 0,28	<0,001
Actinobacteria	3,75%	4,9%	-0,15; 0,14	0,951
Euryarchaeota	1,28%	1,52%	-0,42; 0,1	0,204
Verrucomicrobia	1,29%	0,83%	-0,09; 0,32	0,223

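### The antiphospholipid results treat overlapping 95% confidence intervals as proof of non-significance; this is not a valid test and not one the SAP names

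*Combined protocol and SAP*

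**What the plan says.** In the Statistical Analysis Plan, under Antiphospholipid antibodies, the intervals are planned as description: "The 95% confidence interval for aPL value was calculated for both median and mean". A rank formula for the median interval follows, with no rule for judging significance from overlap. The tests come next. If the data are normal, "the Student's paired t-test was used to determine statistical significance between values before and after freeze-dried mare's milk". For data that are not normal, the SAP turns to a rank test: "If not, the Wilcoxon sign rank criterion was used for intergroup comparison". One-way ANOVA is named for relating aPL levels to the milk in both groups.

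In the Results section, Antiphospholipid antibody analysis, three statements matter:

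- Above Table 8: "After bringing the variables to the normal distribution, the statistical significance was found in the control group only". The table gives control-group p=0.001 (IgM) and 0.0001 (IgG), and main-group p=0.185 and 0.726.
- Table 9 gives one-way ANOVA p-values of 0.541 (IgM) and 0.938 (IgG), with no estimate or interval.
- Below Table 9: "The intersection of all confidence intervals of medians and means indicates the absence of statistical significance between these indicators". The text goes on: "The results before and after bringing the aPL values to normal distribution differ greatly, especially for the IgM level in the main group". It then adds: "One-factor analysis of variance also showed the lack of significance of the studied factor".

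**The concern.** The sentence below Table 9 works as a decision rule: separate intervals intersect, therefore nothing is significant. Overlap of two separate 95% intervals does not show that. The rule ignores how the standard error of a difference is formed, and for before/after data it also ignores the correlation between a patient's two measurements.

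The ANOVA is then introduced as also showing no significance, so the overlap statement reads as independent support for the null antibody conclusion. It cannot carry that weight. Without it, the visible between-arm support is two p-values. A reader of Table 9 cannot tell whether a meaningful arm difference has been excluded or merely not detected.

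**Working it through.** **Inputs.** There are 30 patients per arm (Study Design, Enrollment), so each mean interval has 29 df and t29=2.0452. The Table 8 intervals and p-values are used as printed. Equal SDs and the before/after correlations r are assumptions, since the documents give neither.

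**Reproducing Table 8.** T = midpoint / (half-width / 2.0452), two-sided p on 29 df. The range moves each limit by ±0.005 to allow for rounding.

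| Row | 95% CI | p from CI (range) | Stated p |
|---|---|---|---|
| Control IgM | 0.04; 0.14 | 0.0009 (0.0003–0.0023) | 0.001 |
| Control IgG | 0.05; 0.15 | 0.0003 (0.00009–0.0009) | 0.0001 |
| Main IgM | -0.03; 0.11 | 0.25 (0.20–0.31) | 0.185 |
| Main IgG | -0.07; 0.11 | 0.65 (0.57–0.74) | 0.726 |

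Three rows agree within rounding. For main-group IgM, 0.04/(0.07/2.0452) = 1.17, so p=0.25. The stated 0.185 falls just outside the range, and the row is non-significant either way.

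**What just-touching mean intervals imply.** Each half-width is t29·s/√30, so at the point of contact the difference is 2·t29·s/√30. The standard error of a paired difference is s·√(2(1−r)/30), which gives T = 2·t29/√(2(1−r)).

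| Comparison | T | p |
|---|---|---|
| Two independent arms (58 df) | 4.0904/√2 = 2.89 | 0.005 |
| Paired, r=0 (29 df) | 4.0904/√2 = 2.89 | 0.007 |
| Paired, r=0.3 | 4.0904/√1.4 = 3.46 | 0.0017 |
| Paired, r=0.5 | 4.0904/√1 = 4.09 | 0.0003 |

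Put differently, a paired difference reaches p<0.05 once it exceeds √(2(1−r)) half-widths: 1.41, 1.18 and 1.00 at r=0, 0.3 and 0.5. The intervals do not separate until it exceeds 2.

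**Adding the median intervals does not help.** The SAP formula gives C = 30/2 − 2.045·√30/2 = 9.40. Depending on rounding, the limits are ranks 9 and 22 (exact coverage 98.4%) or 10 and 21 (95.7%). In simulation (200,000 normal samples per case, equal SDs, true difference with 80% power), the mean intervals and the median intervals both still overlapped in 36–38% of samples with p<0.05 for two arms. For paired data the shares were 34–36%, 59–61% and 79–82% at r=0, 0.3 and 0.5. These figures describe the rule; they do not estimate what happened in this trial.

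**Can overlap coexist with Table 8?** Setting the observed T against the touching condition, mean intervals overlap when r > 1 − (2·t29/T)²/2.

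- Control IgM: T = 0.09/0.02445 = 3.68, so r > 0.38 (0.25–0.50 with rounding).
- Control IgG: T = 0.10/0.02445 = 4.09, so r > 0.50, or 0.59 using the T of 4.51 implied by the stated p (0.40–0.60 with rounding).

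With equal SDs at both visits, overlap and the reported p-values are therefore compatible at moderate correlations.

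**The case against.** The strongest objection is that nothing changes. The report uses ANOVA for the direct effect of the product, that result is null, and no antibody benefit is claimed. That stands, and it limits the weight of the point. It does not make the sentence valid, because the sentence is offered as a further reason for the conclusion.

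A second objection is that the results between Table 5 and Table 8 were not available for this review, so the intervals cannot be inspected and the meaning of the indicators cannot be settled. This also stands as far as it goes. Those results could show whether the intervals overlap; they cannot turn overlap into a test.

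A reader might infer that the overlap sentence contradicts the control-group p-values in Table 8. The documents do not support that. If the sentence refers to the arms, there is no direct conflict. If it refers to before/after values, both statements can be true, as the correlation thresholds show. The report itself says that results before and after transformation differ, and the unavailable results may explain why.

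A reader might also infer that a paired test was run across the two arms, because the SAP ties the signed-rank test to intergroup comparison. As written, that would be invalid for independent arms. It is more probably a slip: the clause follows directly from a before/after test, the microbiota and quality-of-life sections use the same fallback for before/after values, and no visible antibody result applies it across arms.

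Finally, the magnitudes rest on assumed correlations, equal SDs and normal data. That is fair. They show how badly the rule can mislead, not how far it did so here.

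**Conclusion.** The concern holds as a fault of inference. Overlap of separate 95% intervals cannot establish absence of significance: at n=30 with equal SDs, touching mean intervals already mean p of about 0.005 between arms and 0.007 to 0.0003 for paired data at assumed correlations of 0 to 0.5. The SAP names no such rule.

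It does not follow that the antibody conclusion is wrong. The Table 9 null is untouched; the consequence lies in how the conclusion is supported and worded. It should be corrected, but it does not reverse a result. The signed-rank wording and the main-group IgM row are minor points beside it.

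**What to change.** 1. Delete the overlap sentence below Table 9.
2. Base the antibody conclusion on the between-arm comparison and say that no arm difference was shown. Beside Table 9, give an estimate with 95% CI from an ANCOVA of the week-4 value on arm and baseline, on the same scale in both arms and labelled post hoc. Deleting the sentence does not depend on this, but the estimate gives the conclusion a valid and informative basis.
3. State whether the transformed or untransformed within-arm result governs, unless the results between Table 5 and Table 8 already do.
4. Minor: confirm how the signed-rank test was actually used. If it was for before/after change within each arm, correct the intergroup wording in the SAP.
5. Minor: check the interval and p-value in the main-group IgM row of Table 8.

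The cost is one deletion, a reworded conclusion, a sentence on scale, two checks and one short re-run on data already collected.
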